### **6.2.1. Preparation and Dispensing**

Within this protocol, preparation refers to the investigator site activities performed to make the study intervention ready for administration or dispensing to the participant by qualified staff. Dispensing is defined as the provision of study intervention, concomitant treatments, and accompanying information by qualified staff member(s) to a healthcare provider, participant, in accordance with this protocol. Local health authority regulations or investigator site guidelines may use alternative terms for these activities.

Tablets/capsules/solution will be prepared at the CRU in the individual dosing containers by 2 operators, 1 of whom is an appropriately qualified and experienced member of the study

staff (eg, physician, nurse, physician's assistant, nurse practitioner, pharmacy assistant/technician, or pharmacist). The tablets, capsules, or solution will be provided in unit dose containers and labeled in accordance with Pfizer regulations and the clinical site's labeling requirements.

### **6.3. Assignment to Study Intervention**

The investigator's knowledge of the treatment should not influence the decision to enroll a particular participant or affect the order in which participants are enrolled.

The investigator will assign participant numbers to the participants as they are screened for the study. Pfizer will provide a randomization schedule to the investigator and, in accordance with the randomization numbers, the participant will receive the study treatment regimen assigned to the corresponding randomization number.

### **6.4. Blinding**

This is an open label study.

### **6.5. Study Intervention Compliance**

When the individual dose for a participant is prepared from a bulk supply, the preparation of the dose will be confirmed by a second qualified member of the study site staff.

When participants are dosed at the site, they will receive study intervention directly from the investigator or designee, under medical supervision. The date and time of each dose administered in the clinic will be recorded in the source documents and recorded in the CRF. Study site personnel will examine each participant's mouth to ensure that the study intervention was ingested.

### **6.6. Dose Modification**

Dose modification will not be permitted in this study for any study intervention.

### **6.7. Continued Access to Study Intervention After the End of the Study**

No study intervention will be provided to participants at the end of their study participation. It is expected that participants will be treated as required with standard-of-care treatments, as advised by their usual care physician.

### **6.8. Treatment of Overdose**

For this study, any dose of PF-07081532 greater than 1.6 g within a 24-hour time period will be considered an overdose. A single dose of 1.6 g is projected to result in exposure that will exceed that observed at the NOAEL in the pivotal 9-month toxicology study in monkeys, after accounting for species differences in plasma protein binding.

For this study, overdose for itraconazole or cyclosporine will be as per the USPI labels.

There is no specific treatment for an overdose of PF-07081532. Treatment of overdose should consist of general supportive measures.

In the event of an overdose, the investigator should:

1. Contact the study medical monitor within 24 hours.
2. Closely monitor the participant for any AEs/SAEs and laboratory abnormalities as medically appropriate and at least until the next scheduled follow-up.
3. Document the quantity of the excess dose as well as the duration of the overdose in the CRF.
4. Overdose is reportable to Pfizer Safety **only when associated with an SAE**.
5. Obtain a blood sample for PK analysis within 1 day from the date of the last dose of study intervention if requested by the study medical monitor (determined on a case-by-case basis).

Decisions regarding dose interruptions or modifications will be made by the investigator in consultation with the study medical monitor as needed based on the clinical evaluation of the participant.

### **6.9. Prior and Concomitant Therapy**

Study participants will abstain from all concomitant treatments, except for the treatment of AEs, as described in the [Exclusion Criteria](#) section of this protocol.

Use of prescription or nonprescription drugs and dietary and herbal supplements are prohibited within 7 days or 5 half-lives (whichever is longer) prior to the first dose of study intervention.

Systemic therapy with moderate or strong CYP3A4/5 and/or CYP2C19 inhibitors or inducers within 14 days or 5 half-lives (whichever is longer) prior to the first dose of study intervention are prohibited. Systemic therapy with inhibitors of OATP transporters within 14 days or 5 half-lives (whichever is longer) prior to the first dose of study intervention are prohibited.

Use of a GLP-1R agonist is prohibited within 90 days prior to the first dose of study intervention, with the exception of PF-07081532, which is prohibited within 30 days prior to the first dose of study drug.

Limited use of nonprescription medications that are not believed to affect participant safety or the overall results of the study may be permitted on a case-by-case basis following approval by the sponsor. Acetaminophen/paracetamol may be used at doses of  $\leq 1$  g/day.

Anti-emetics (eg, prochlorperazine, promethazine, ondansetron) may be administered at the investigator's discretion with notification to the sponsor and entry in the CRF.

Sites are encouraged to contact the sponsor should there be questions as to whether a medication is permitted or prohibited.

Implantable progestogen or intrauterine hormone releasing system only are allowed to be used in participants who are WOCBP (see [Appendix 4](#)).

Females using hormonal contraceptives that do not meet the requirements of this study or who are taking hormone replacement therapy may be eligible to participate in this study if they are willing to discontinue therapy at least 28 days prior to the first dose of study treatment and remain off hormonal therapy for the duration of the study. Depo-Provera® must be discontinued at least 6 months prior to the first dose of study treatment.

All concomitant treatments taken during the study must be recorded with indication, daily dose, and start and stop dates of administration. All participants will be questioned about concomitant treatment at each clinic visit.

Treatments taken within 28 days before the first dose of study intervention will be documented as a prior treatment. Treatments taken after the first dose of study intervention will be documented as concomitant treatments.

### **6.9.1. Rescue Medicine**

There is no rescue therapy to reverse the AEs observed with PF-07081532; standard medical supportive care must be provided to manage the AEs, including administration of carbohydrates to treat HAEs (see [Section 8.3.6](#)).

#### **6.9.1.1. Management of Nausea and Vomiting**

Nausea and vomiting have been reported with administration of GLP-1R agonists and also with administration of PF-07081532 (see [Section 2.2.4](#)). Study participants complaining of nausea may be managed conservatively with bed rest and/or fluid management at the discretion of the investigator. If nausea and vomiting are not amenable to conservative management, anti-emetics (eg, prochlorperazine, promethazine, ondansetron) may be administered at the investigator's discretion with notification to the sponsor and entry in the CRF.

## **7. DISCONTINUATION OF STUDY INTERVENTION AND PARTICIPANT DISCONTINUATION/WITHDRAWAL**

### **7.1. Discontinuation of Study Intervention**

It may be necessary for a participant to permanently discontinue study intervention. Reasons for permanent discontinuation of study intervention include the following:

- Criteria for a potential Hy's law case are met (see [Appendix 6](#)).
- Intent to become pregnant or pregnancy confirmed by serum  $\beta$ -hCG testing.

- Safety or tolerability concern arises, in particular, if not responsive to symptomatic management, dosing with study intervention may be stopped in an individual participant at investigator discretion.
- Based on mental health assessment as outlined in [Section 8.3.8](#), should be discontinued from dosing at investigator discretion.
- Positive SARS-CoV-2 Test.

If the criteria for permanent discontinuation are met, the site should notify the sponsor Medical Monitor or sponsor Clinician.

Note that discontinuation of study intervention does not represent withdrawal from the study. If study intervention is permanently discontinued, the participant should remain in the study to be evaluated for safety. See the [SoA](#) for data to be collected at the time of discontinuation of study intervention and follow-up for any further evaluations that need to be completed.

In the event of discontinuation of study intervention, it must be documented on the appropriate CRF/in the medical records whether the participant is discontinuing further receipt of study intervention or also from study procedures, post-treatment study follow-up, and/or future collection of additional information.

#### **7.1.1. Potential Cases of Acute Kidney Injury**

Abnormal values in Scr concurrent with presence or absence of increase in BUN that meet the criteria below, in the absence of other causes of kidney injury, are considered potential cases of acute kidney injury and should be considered important medical events.

An increase of  $\geq 0.3$  mg/dL (or  $\geq 26.5$   $\mu\text{mol/L}$ ) in Scr level relative to the participant's own baseline measurement should trigger another assessment of Scr as soon as practically feasible, preferably within 48 hours from awareness.

If the second assessment (after the first observations of  $\geq 0.3$  mg/dL [or  $\geq 26.5$   $\mu\text{mol/L}$ ] in Scr relative to the participant's own baseline measurement) is  $\geq 0.4$  mg/dL (or  $\geq 35.4$   $\mu\text{mol/L}$ ), the participant should be discontinued from the study and adequate, immediate, supportive measures taken to correct apparent acute kidney injury.

Participants should return to the investigator site and be evaluated as soon as possible, preferably within 48 hours from awareness of the second assessment confirming abnormal Scr result. This evaluation should include laboratory tests, detailed history, and physical assessment. In addition to repeating Scr, laboratory tests should include serum BUN, serum creatine kinase, and serum electrolytes (including at a minimum potassium, sodium, phosphate/phosphorus, and calcium), in addition to urinary dipstick, urine microscopic examination, and urinary indices. All cases confirmed on repeat testing as meeting the laboratory criteria for acute kidney injury, with no other cause(s) of laboratory abnormalities identified, should be considered potential cases of drug-induced kidney injury irrespective of availability of all the results of the investigations performed to determine etiology of the

abnormal Scr. If  $\geq 2$  healthy participants in a given period are noted to have 2 *consecutive* Scr results of  $\geq 0.3$  mg/dL (or  $\geq 26.5$   $\mu\text{mol/L}$ ), an assessment of whether the finding may be considered an adverse drug reaction should be undertaken.

## **7.2. Participant Discontinuation/Withdrawal From the Study**

A participant may withdraw from the study at any time at their own request. Reasons for discontinuation from the study include the following: safety, behavioral, compliance, administrative reasons, and/or if the study is terminated by the sponsor.

At the time of discontinuing from the study, if possible, an early discontinuation visit should be conducted. See the [SoA](#) for assessments to be collected at the time of study discontinuation and follow-up and for any further evaluations that need to be completed.

The early discontinuation visit applies only to participants who are enrolled/randomized and then are prematurely withdrawn from the study. Participants should be questioned regarding their reason for withdrawal.

The participant will be permanently discontinued from the study intervention and the study at that time.

If a participant withdraws from the study, they may request destruction of any remaining samples taken and not tested, and the investigator must document any such requests in the site study records and notify the sponsor accordingly.

If the participant withdraws from the study and also withdraws consent (see Section 7.2.1) for disclosure of future information, no further evaluations will be performed and no additional data will be collected. The sponsor may retain and continue to use any data collected before such withdrawal of consent.

### **7.2.1. Withdrawal of Consent**

Participants who request to discontinue receipt of study intervention will remain in the study and must continue to be followed for protocol-specified follow-up procedures. The only exception to this is when a participant specifically withdraws consent for any further contact with them or persons previously authorized by the participant to provide this information. Participants should notify the investigator in writing of the decision to withdraw consent from future follow-up, whenever possible. The withdrawal of consent should be explained in detail in the medical records by the investigator, as to whether the withdrawal is only from further receipt of study intervention or also from study procedures and/or posttreatment study follow-up, and entered on the appropriate CRF page. In the event that vital status (whether the participant is alive or dead) is being measured, publicly available information should be used to determine vital status only as appropriately directed in accordance with local law.

## **7.3. Lost to Follow-up**

A participant will be considered lost to follow-up if the participant repeatedly fails to return for scheduled visits and is unable to be contacted by the study site.

The following actions must be taken if a participant fails to attend a required study visit:

- The site must attempt to contact the participant and reschedule the missed visit as soon as possible. Counsel the participant on the importance of maintaining the assigned visit schedule and ascertain whether the participant wishes to and/or should continue in the study;
- Before a participant is deemed lost to follow-up, the investigator or designee must make every effort to regain contact with the participant (where possible, 3 telephone calls and, if necessary, a certified letter to the participant's last known mailing address or local equivalent methods). These contact attempts should be documented in the participant's medical record;
- Should the participant continue to be unreachable, the participant will be considered to have withdrawn from the study.

## **8. STUDY ASSESSMENTS AND PROCEDURES**

### **8.1. Administrative Procedures**

The investigator (or an appropriate delegate at the investigator site) must obtain a signed and dated ICD before performing any study-specific procedures.

Study procedures and their timing are summarized in the [SoA](#). Protocol waivers or exemptions are not allowed.

Adherence to the study design requirements, including those specified in the [SoA](#), is essential and required for study conduct.

All screening evaluations must be completed and reviewed to confirm that potential participants meet all eligibility criteria. The investigator will maintain a screening log to record details of all participants screened and to confirm eligibility or record reasons for screening failure, as applicable.

Participants will be screened within 28 days prior to administration of the study intervention to confirm that they meet the study population criteria for the study. If the time between screening and dosing exceeds 28 days as a result of unexpected delays (eg, delayed drug shipment), then participants do not require rescreening if the laboratory results obtained prior to first dose administration meet eligibility criteria.

A participant who qualified for this protocol but did not enroll from an earlier cohort/group may be used in a subsequent cohort/group without rescreening, provided laboratory results obtained prior to the first dose administration meet eligibility criteria for this study. In addition, other clinical assessments or specimen collections, eg, retained research samples, may be used without repeat collection, as appropriate.

Every effort should be made to ensure that protocol-required tests and procedures are completed as described. However, it is anticipated that from time to time there may be

circumstances outside the control of the investigator that make it unfeasible to perform the test. In these cases, the investigator must take all steps necessary to ensure the safety and well-being of the participant. When a protocol-required test cannot be performed, the investigator will document the reason for the missed test and any corrective and preventive actions that they have taken to ensure that required processes are adhered to as soon as possible. The study team must be informed of these incidents in a timely manner.

If an IV catheter is utilized for blood sample collections, ECGs and vital sign assessments (pulse rate and BP) should be collected prior to the insertion of the catheter.

For samples being collected and shipped, detailed collection, processing, storage, and shipment instructions and contact information will be provided to the investigator site prior to initiation of the study.

The total blood sampling volume for individual participants in this study is approximately 200 mL. The actual collection times of blood sampling may change. Additional blood samples may be taken for safety assessments at times specified by Pfizer, provided the total volume taken during the study does not exceed 550 mL during any period of 56 consecutive days.

To prepare for study participation, participants will be instructed on the information in the [Lifestyle Considerations](#) and [Prior and Concomitant Therapy](#) sections of the protocol.

## **8.2. Efficacy Assessments**

Efficacy is not evaluated in this study.

## **8.3. Safety Assessments**

Planned time points for all safety assessments are provided in the [SoA](#). Unscheduled safety measurements may be obtained at any time during the study to assess any perceived safety issues.

### **8.3.1. Physical Examinations**

A complete physical examination will include, at a minimum, head, ears, eyes, nose, mouth, skin, heart and lung examinations, lymph nodes, and gastrointestinal, musculoskeletal, and neurological systems.

A brief physical examination will include, at a minimum, assessments of general appearance, the respiratory and cardiovascular systems, and participant -reported symptoms.

Physical examinations may be conducted by a physician, trained physician's assistant, or nurse practitioner as acceptable according to local regulation.

Height and weight will also be measured and recorded as per the [SoA](#). For measuring weight, a scale with appropriate range and resolution is used and must be placed on a stable, flat surface. Participants must remove shoes, bulky layers of clothing, and jackets so that only

light clothing remains. They must also remove the contents of their pockets and remain still during measurement of weight.

Physical examination findings collected during the study will be considered source data and will not be required to be reported, unless otherwise noted. Any untoward physical examination findings that are identified during the active collection period and meet the definition of an AE or SAE ([Appendix 3](#)) must be reported according to the processes in [Section 8.4.1](#) to [Section 8.4.3](#).

### **8.3.2. Vital Signs**

#### **8.3.2.1. Blood Pressure and Pulse Rate**

Supine BP will be measured with the participant's arm supported at the level of the heart and recorded to the nearest mm Hg after approximately 5 minutes of rest. The same arm (preferably the dominant arm) will be used throughout the study. Participants should be instructed not to speak during measurements. If triplicate measurements are obtained, they should be collected approximately 2 minutes apart.

The same properly sized and calibrated BP cuff will be used to measure BP each time. The use of an automated device for measuring BP and pulse rate is acceptable; however, when done manually, pulse rate will be measured in the brachial/radial artery for at least 30 seconds. When the timing of these measurements coincides with a blood collection, BP and pulse rate should be obtained prior to the nominal time of the blood collection.

Additional collection times, or changes to collection times, of BP and pulse rate will be permitted, as necessary, to ensure appropriate collection of safety data.

Any untoward vital sign findings that are identified during the active collection period and meet the definition of an AE or SAE ([Appendix 3](#)) must be reported according to the processes in [Section 8.4.1](#) to [Section 8.4.3](#).

#### **8.3.2.2. Temperature**

Temperature will be measured orally at Screening. No eating, drinking, or smoking is allowed for 15 minutes prior to the measurement.

#### **8.3.3. Electrocardiograms**

Standard 12-lead ECGs utilizing limb leads (with a 10-second rhythm strip) should be collected at times specified in the [SoA](#) of this protocol using an ECG methodology that automatically calculates the HR and measures PR interval, QT interval, QTcF, and QRS complex. All scheduled ECGs should be performed after the participant has rested quietly for at least 5 minutes in a supine position.

To ensure safety of the participants, a qualified individual at the investigator site will make comparisons to baseline measurements. Additional ECG monitoring will occur if a) a postdose QTcF interval is increased by  $\geq 60$  ms from the baseline **and** is  $>450$  ms; or b) an absolute QT value is  $\geq 500$  ms for any scheduled ECG. If either of these conditions occurs,

then 2 additional ECGs will be collected approximately 2 to 4 minutes apart to confirm the original measurement. If the QTcF values from these repeated ECGs remain above the threshold value, then a single ECG must be repeated at least hourly until QTc values from 2 successive ECGs fall below the threshold value that triggered the repeat measurement.

If a) a postdose QTcF interval remains  $\geq 60$  ms from the baseline **and** is  $> 450$  ms; or b) an absolute QT value is  $\geq 500$  ms for any scheduled ECG for greater than 4 hours (or sooner, at the discretion of the investigator); or c) QTcF value get progressively longer, the participant should undergo continuous ECG monitoring. A cardiologist should be consulted if QTcF values do not return to less than the criteria listed above after 8 hours of monitoring (or sooner, at the discretion of the investigator).

In some cases, it may be appropriate to repeat abnormal ECGs to rule out improper lead placement as contributing to the ECG abnormality. It is important that leads be placed in the same positions each time in order to achieve precise ECG recordings. If a machine-read QTc value is prolonged, as defined above, repeat measurements may not be necessary if a qualified medical provider's interpretation determines that the QTcF values are in the acceptable range.

ECG values of potential clinical concern are listed in [Appendix 8](#).

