#### 9.3.2.1. Electrocardiogram Analyses

Changes from baseline for the ECG parameters HR, QTcF, PR interval, and QRS complex will be summarized by period and time. The frequency of uncorrected QT values above 500 ms will be tabulated.

The number (%) of participants with maximum postdose QTcF values and maximum increases from baseline in the following categories will be tabulated by period:

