#### Safety QTcF Assessment

Degree of Prolongation	Mild (ms)	Moderate (ms)	Severe (ms)
Absolute value	>450-480	>480-500	>500
Increase from baseline		30-60	>60

Baseline will be pre-dose on Day 1.

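### Protocol 8.3.3 triggers repeat ECGs on uncorrected QT ≥500 ms but judges them on QTcF, and no limb triggers on an absolute QTcF above 500 ms

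*Protocol*

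**What the plan says.** Protocol 8.3.3 sets two triggers for extra ECGs after dosing. Limb (a) needs both a QTcF rise of at least 60 ms from baseline and a QTcF above 450 ms. Limb (b) reads "b) an absolute QT value is" 500 ms or more. Either one leads to two further recordings a few minutes apart.

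The later steps are worded as follows:

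- **Confirmation:** "If the QTcF values from these repeated ECGs remain above the threshold value", hourly ECGs begin.
- **Stopping:** they continue "until QTc values from 2 successive ECGs fall below the threshold value that triggered the repeat measurement".
- **Continuous monitoring:** limbs (a) and (b) are restated with a 4-hour duration, again with QT in limb (b). A limb (c) is added for QTcF that keeps lengthening, with no fixed threshold.
- **Referral:** "A cardiologist should be consulted if QTcF values do not return to less than the criteria listed above" after 8 hours of monitoring.
- **Over-read:** "repeat measurements may not be necessary if a qualified medical" provider judges the QTcF acceptable.

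The protocol treats QT and QTcF as separate measures. The ECG method in 8.3.3 "automatically calculates the HR and measures PR interval, QT interval, QTcF, and QRS complex". Section 9.3.2.1 says "The frequency of uncorrected QT values above 500 ms will be tabulated", and then sets out a separate table headed "Safety QTcF Assessment" in which QTcF above 500 ms is Severe. SAP 6.5.5 repeats both. Appendix 8 lists QTcF above 500 ms among findings that may qualify as SAEs.

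**The concern.** There are two related wording faults.

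1. **The variable changes mid-rule.** The threshold for limb (b) is a QT value, but confirmation and referral compare QTcF with it, and stopping compares a QTc whose correction is not named. A participant can meet limb (b), show the same QT on both repeats, and still fail confirmation. Hourly ECGs are then not mandated, yet the 4-hour step asks whether QT has stayed at 500 ms or more.

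2. **No limb uses absolute QTcF.** Limb (a) depends on the rise from baseline and limb (b) on uncorrected QT. A reading in the study's own Severe category can pass between them, so 8.3.3 does not mandate even the two repeat ECGs.

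What is at stake is whether a safety rule works on the few occasions when a scheduled ECG is abnormal. The primary PK analysis is not involved.

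**Working it through.** The plan gives no figure to reproduce. The check applies its thresholds with the SAP's own formula.

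**Inputs**

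- Limb (a): rise ≥60 ms and QTcF >450 ms. Limb (b): QT ≥500 ms (Protocol 8.3.3).
- QTcF = QT / RR^(1/3), with RR = 60/HR (SAP 3.5.5). Hence QT = QTcF × (60/HR)^(1/3).
- Baseline is pre-dose on Day 1 (Protocol 9.3.2.1; Period 1 in SAP 3.5.5), with no QTcF limit stated for that day. The Screening limit is 450 ms, given as an example in exclusion criterion 22.
- Readings are taken as whole milliseconds.

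**Step 1: what limb (a) misses.** Any QTcF above 500 ms already exceeds 450 ms, so limb (a) is missed when QTcF − baseline ≤ 59. The lowest case is QTcF 501 ms, which needs a baseline of at least 501 − 59 = 442 ms. The top of the band is baseline + 59, or 509 ms at baseline 450 ms.

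**Step 2: what limb (b) misses.** QT is below 500 ms when HR > 60 × (QTcF/500)³.

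**Step 3: both together.**

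| QTcF (ms) | Limb (a) missed if baseline is at least | Limb (b) missed if HR is above |
|---|---|---|
| 501 | 442 ms | 60.4 bpm |
| 505 | 446 ms | 61.8 bpm |
| 509 | 450 ms | 63.3 bpm |
| 514 | 455 ms (assumed) | 65.2 bpm |
| 519 | 460 ms (assumed) | 67.1 bpm |

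The first three rows keep the baseline within the Screening limit. The last two show how the band widens if the Day 1 baseline exceeds it. At 60 bpm or below, limb (b) catches every QTcF above 500 ms.

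Example: baseline 448 ms, QTcF 505 ms, 70 bpm. The rise is 505 − 448 = 57 ms, so limb (a) does not fire. QT = 505 × (60/70)^(1/3) = 479.7 ms, so limb (b) does not fire.

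**Step 4: the change of variable.** With QT 500 ms, QTcF = 500 / (60/HR)^(1/3):

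- 45 bpm: 454.3 ms
- 50 bpm: 470.5 ms
- 55 bpm: 485.7 ms

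In each case limb (b) fires, but QTcF is already under 500 ms at confirmation.

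**Step 5: with limb (b) as QTcF ≥500 ms.** Every QTcF above 500 ms triggers, whatever the baseline or heart rate, and the gap in Step 3 closes.

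**Step 6: how often it could arise.** Table 1 schedules ECGs pre-dose on Day 1 of each period and before discharge. Three of these follow first dosing: 16 participants × 3 = about 48 ECGs. Study Day 1 to 6 and Study Day 6 to 11 are each 120 h after a PF-07081532 dose; Period 3 Day 4 to Day 10 is 144 h. At the mean half-lives of 18.03–26.50 h in Protocol 2.2.4.1, reported without an inhibitor, this is 120/26.50 = 4.5 to 144/18.03 = 8.0 half-lives. The documents give no frequency for the combinations in Step 3.

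**The case against.** The best reply is that QT in limb (b) is a slip of one word. Confirmation, stopping, limb (c), referral and over-read all speak of QTcF or QTc, and the over-read sentence describes the triggers already defined as prolonged QTc. On that reading one substitution removes both faults. This is persuasive and shapes the fix. But the text to be followed says QT, twice, in a protocol that elsewhere treats uncorrected QT as its own quantity, so it still needs correcting.

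If uncorrected QT was deliberate, a raw-QT screen followed by a rate-corrected check is coherent. QT 500 ms at 50 bpm has a QTcF of about 471 ms, only Mild in 9.3.2.1, and not ordering hourly ECGs for it is reasonable. That also stands. A reader might infer that every later step should be judged on QT whenever QT triggered. The documents do not support this: it would escalate slow heart rates with modest QTcF and would conflict with an over-read decided on QTcF. The absence of an absolute QTcF limb remains on this reading.

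A reader might also infer that a QTcF above 500 ms would go unaddressed. The documents do not support that either. A qualified person compares ECGs with baseline, unscheduled measurements are allowed (8.3), Appendix 8 recommends alerts, and recorded AEs are followed up (8.4.3, Appendix 3). These routes depend on judgment and set no repeat timing, so they soften the gap without supplying the mandated repeat.

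**Conclusion.** The point holds as a minor correction to a safety rule. Limb (b) of 8.3.3 and the steps after it use different variables. As written, a QTcF above 500 ms with a rise below 60 ms and a heart rate above about 60–63 bpm has no mandated repeat ECG.

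The 501–509 ms band, and the heart-rate range that goes with it, assume a Day 1 baseline of at most 450 ms. It should not be read as a fixed limit: no Day 1 ceiling is stated, and a higher baseline widens the band.

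The practical effect is small. There are about 48 scheduled ECGs after first dosing, all 120 or 144 h after a PF-07081532 dose. Nothing here touches PK sampling or the PK analysis.

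**What to change.** In both places in 8.3.3, write limb (b) as *an absolute QTcF value is ≥500 ms*. In the stopping sentence, write QTcF for QTc. Trigger, confirmation, stopping, the 4-hour step, referral and over-read then all use one variable. The ≥500 ms cut keeps the number already in limb (b) and covers the whole Severe band, plus exactly 500 ms, which 9.3.2.1 classes as Moderate.

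If the sponsor also wants a raw-QT screen at ≥500 ms, keep it as an additional trigger for the two repeat ECGs only, with every later step judged on QTcF. Without it, a QT of 500 ms or more at a slow heart rate with QTcF below 500 ms would no longer prompt repeats unless limb (a) fires.

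The cost is a wording change in one section and at most a few extra ECGs. Appendix 8, Protocol 9.3.2.1 and SAP 6.5.5 need no change.
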